## Appendix C

### Post-Test

1. Using vaping products will help you stop smoking cigarettes?
  - a. True
  - b. False
2. Using vaping products may cause harm to my health?
  - a. True
  - b. False
3. By using vaping products, I am more likely to smoke cigarettes in the future.
  - a. True
  - b. False
4. There are currently \_\_\_\_ million students that use vaping products
  - a. 1 million
  - b. 3.5 million
  - c. 8 million
  - d. 5.3 million
5. Students who vape are \_\_\_\_ more likely to begin smoking cigarettes
  - a. twice
  - b. four times
  - c. five times
  - d. ten times
6. There are at least \_\_\_\_ confirmed vape related deaths as of January 21st, 2020
  - a. 15
  - b. 35
  - c. 60
  - d. 2
7. People vape because \_\_\_\_
  - a. It helps them to relax
  - b. Their friends or family vape
  - c. They like the taste of it
  - d. They think it is safer than tobacco cigarettes
  - d. All the above
8. I feel pressured to vape.
  - a. Yes
  - b. No
  - c. Sometimes

9. Effects that vaping has on my body are \_\_\_\_\_

- a. Decreased brain development
- b. Problems with breathing
- c. Increase heart rate
- d. Higher chance of developing cancer
- e. All the above

10. How likely are you to use vaping products?

- a. Not at all
- b. Not sure
- c. Very likely
- d. I already vape

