Many vaping companies present their products as nicotine free and as being a safe and non-addictive way of smoking. From commercials to online ads, consumers are being told that this product is free from the smell of cigarettes, reusable, much cheaper, and even healthier than traditional cigarettes. This information can be very deceiving and persuasive to the young mind.

This program titled, “To Vape or Not to Vape”, will provide education to adolescents and young adults about the potential risk of vaping in an effort to assist with lowering the usage rates within the population. Content will include information about current statistics, potential short-term and long-term side-effects, and healthy alternatives for dealing with stress and peer-pressure. We anticipate that this program will increase this population’s knowledge about the risks of vaping products, and deter them from future use of the products. Effectiveness of this program will be measured by pre and post-tests.

**1.2.** Aim(s)/Objective(s)

The overall goal of this study is to increase knowledge of vaping and its associated risks. This study will find the patterns of vaping, and how it all started among adolescents. We want to know if students are aware of the serious and long term effects of vaping.

The objectives are:

1. To provide at least 100 middle school and high school students with anti-vaping education.
2. To provide at least 40 college students with anti-vaping education.
3. To improve the overall knowledge of vaping statistics and side effects as measured by a pre and post-test. The pre-test will be the baseline measurement. The post-test will be the measure of effectiveness. Out of the 10 questions on the post-test, the goal is to have the students answer at least 8 out of the 10 questions correctly.
4. To decrease the percentage of students who say that they are likely to vape in the future.

The program will be going to middle school, high school, and college campuses in the Dallas-Fort Worth (DFW) area to speak with students about vaping. The program will be implemented by community outreach, as the students will be presented with information about vaping and the resources necessary to prevent or stop vaping. This program will present the students with a 35-minute curriculum that is listed below. The purpose of this study is to relay

and publish data that will support education about vaping and the many health risks associated with vaping products.

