### **1.3.** Rationale for the study

The Food and Drug Administration (FDA), has yet to release any proven reviews and standards on the components of e-cigarettes, nor the long- term effects of vaping (ALA, 2019). However, researchers have noticed the toxic chemicals and metals found in e-cigarettes. A few of the chemicals include nicotine, cancer causing carcinogens, and heavy metals such as nickel, tin, and lead. Also found in these products is benzene, which a chemical in crude oil and gasoline. There are many more dangerous chemicals in these products that most individuals are unaware of (ALA, 2019). The harsh chemicals found in vaping products, are directly linked to lung disease, difficulty breathing, spikes in blood pressure, rapid heart rate, gum disease, and many more.

This study will address the rise in vape products by providing education that will help prevent and decrease the percentage of students that currently vape.

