### 2.2.2. Secondary Outcome(s)

Changes in the degree of understanding will be assessed from the results of the pre- and post-test (Appendix C). In addition, we hope to find the answers to the following questions:

- Is vaping within the student's environment?
- Are the students being socially peer pressured into smoking, and if so how often?
- Are most students forming addictive behaviors towards vaping?
- What are the triggers that cause a student to vape?
- What is their reasoning on why they vape or participate in any smoking products?
- Do members of their close group of friends' vape?
- Are students aware of the serious and long-term side effects of vaping?

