## **B. E-cigarettes vs. Vapes ([name])**

1. **Electronic cigarettes or better known as E-cigarettes**, are devices that look similar to traditional cigarettes and they are battery-powered device that works by heating a liquid into an aerosol that the user inhales and exhales. E-cigarettes do not contain tobacco. The e-cigarette liquid typically contains propylene glycol, nicotine, glycerin, flavorings, and other harsh chemicals. Nicotine is an addictive drug found in regular cigarettes and other tobacco products.
2. **Vape pens** consist of a rechargeable battery and refillable tank. The e-liquid in vaporizer products does not contain tobacco. The public makes it seem like vape products only have flavored water in them, which is not true! Vape products usually contain a propylene glycol or vegetable glycerin-based liquid with nicotine, flavoring and other harsh chemicals and metals.

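### Five of the seven harm-direction test items are answered correctly by the most anti-vaping option, so part of a pre/post gain may be agreement rather than knowledge; two small edits reduce this

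*Combined protocol and SAP*

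**What the plan says.** Section 1.2, objective 3, sets the aim "To improve the overall knowledge of vaping statistics and side effects as measured by a pre and post-test" and adds that "the goal is to have the students answer at least 8 out of the 10 questions correctly". Section 2.2.2 assesses change in understanding from the same two forms in Appendix C. The design (section 3) is one session of about 35 minutes, with the pre-test before it and the post-test at its end, and no comparison group.

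The ten post-test questions repeat pre-test questions 5 to 14. They include "Using vaping products will help you stop smoking cigarettes" (item 1), "Using vaping products may cause harm to my health" (item 2) and the number of "confirmed vape related deaths as of January 21st, 2020" (item 6). Items 8 and 10 ask about pressure to vape and intention to vape, and have no factual answer.

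The documents contain no answer key, no list of scored items and no definition of a total score. Section 5.2 names a paired t test or Wilcoxon signed-rank test for continuous outcomes and the McNemar test for categorical ones.

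**The concern.** The session argues in one direction, and most of the test rewards answers in that direction. A student who leaves convinced that vaping is bad, but has learned no specific fact, can raise the score by choosing the most negative option each time. With no control group, a paired test on a total score would detect that shift but could not say what it means.

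At stake is the wording of the conclusion. Objective 3 claims knowledge of statistics and side effects, and some of an observed gain might be agreement with the message. Once the data are collected, items that would help tell the two apart cannot be added.

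**Working it through.** The only computed figure in the plan is the sample size. It reproduces: a two-sided Wilcoxon test with a normal parent distribution gives 35, and 35/0.8 = 43.75, rounded up to 44. It does not bear on this point.

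**Step 1: answers, item by item (post-test numbering).**

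| Item (pre-test no.) | Options | Answer | Basis | Most anti-vaping option correct? |
|---|---|---|---|---|
| 1 (5) | 2 | False | Inferred; stated nowhere | Yes |
| 2 (6) | 2 | True | Section 1.3: the chemicals "are directly linked to lung disease, difficulty breathing, spikes in blood pressure, rapid heart rate" | Yes |
| 3 (7) | 2 | True | Section 1.1, fourfold risk of smoking | Yes |
| 4 (8) | 4 | 5.3 million | Section 1.1 | No (8 million offered) |
| 5 (9) | 4 | Four times | Section 1.1 | No (ten times offered) |
| 6 (10) | 4 | 60 | Section 1.1 | Yes (highest offered) |
| 7 (11) | 5 | Not stated | Reasons for vaping | No harm direction |
| 9 (13) | 5 | All the above | Section 1.3; Appendix D II.C | Yes |

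Seven items have a harm direction. In five of them the most anti-vaping option is correct.

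**Step 2: pure guessing on the eight factual items.** 3 × 0.5 + 3 × 0.25 + 2 × 0.2 = 2.65.

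**Step 3: always the most anti-vaping option, item 7 guessed.** Items 1, 2, 3, 6 and 9 give 5, items 4 and 5 give 0, and item 7 gives 0.2, for a total of 5.2. The difference from guessing is 2.55 items, and 2.55/8 = 32 points.

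**Step 4: dependence on the baseline.** The documents give no baseline, so a range is assumed. Let b be the share correct on the five items at pre-test, with items 4 and 5 at chance (0.25 each). A student who moves to the always-alarming pattern changes by 5(1 − b) − 0.5 items on the seven harm-direction items:

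- b = 50%: 2.5 − 0.5 = 2.0
- b = 70%: 1.5 − 0.5 = 1.0
- b = 90%: 0.5 − 0.5 = 0

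On eight items these are 25, 12.5 and 0 points.

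**Step 5: the form with two edits.** Item 3 becomes a True/False item whose alarming answer is wrong, and item 6 gains an option above 60 in place of 2. The numbers of options do not change, so guessing still gives 2.65. The always-alarming student is now right only on items 1, 2 and 9: 3 + 0.2 = 3.2. The difference is 0.55 items, and 0.55/8 = 7 points.

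In the form of step 4, with b now applying to items 1, 2 and 9 and the other four at chance (0.5 + 3 × 0.25 = 1.25), the change is 3(1 − b) − 1.25. That is 0.25 at 50%, −0.35 at 70% and −0.95 at 90%.

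**The case against.** The strongest reply is that the form already contains two items on which exaggeration fails, and that section 5.2 permits item-level McNemar tests, so items 4 and 5 could be read against the others with no change. That stands. A reader might infer that the score cannot separate knowledge from agreement at all; the documents do not support that. But two items are a thin safeguard, and nothing in the plan says they will be read separately.

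Second, the programme sets out to teach the dangers of vaping. Appendix D II.C covers the brain, breathing, heart-rate and cancer effects, so a student who moves to the all-inclusive answer on item 9 has reproduced taught content. This also stands: such a move may be real learning, and nothing in the documents shows how many students answer by direction alone. It is weaker for items 1, 3 and 6, whose answers do not appear in the Appendix D outline as shown, although section 1.1 promises current statistics.

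Third, the 32 points should not be taken as an expected inflation. They require students to guess at pre-test, including a coin flip on whether vaping may cause harm. Step 4 gives the fairer range, down to zero.

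**Conclusion.** The point holds as an inexpensive improvement to the test, not as a flaw that voids the comparison. On the answers the documents support, with item 1 inferred, five of seven harm-direction items reward the most anti-vaping option, so a rise in a total score can partly reflect acceptance of the message. For a student who answers purely by direction, the net effect is about 2.0, 1.0 or 0 items at assumed baselines of 50%, 70% or 90% correct on the five items. The share of such students is unknown.

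A reader might also infer that attitude alone meets the target of 8 out of 10. That is so only if item 7 (all of the listed reasons), item 8 (no pressure) and item 10 (not at all likely) are also counted as correct: 5 + 3 = 8. The plan does not say that they are. On the eight factual items the always-alarming pattern reaches at most 6.

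**What to change.** Make these changes identically on both forms before first use:

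- **Item 3 (pre-test 7).** Its answer is already implied by item 5. Replace it with a scripted fact whose correct answer is not the alarming one, for example a True/False item stating that e-cigarettes contain tobacco. The answer is False, since Appendix D II.B says "E-cigarettes do not contain tobacco".
- **Item 6 (pre-test 10).** Replace option 2 with a number above 60. The item's wording of at least so many deaths also makes the lower options literally true; that is a separate wording matter.
- **Reporting.** Present items 3 (as replaced), 4, 5 and 6 separately from the rest, and describe a gain as knowledge only if it also holds there. Confirm that the session states the figures behind items 4 to 6.

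Splitting item 9 into Yes/No effects with one false effect added may look like a natural further step, but is not recommended. The documents leave the list of harms open, so they supply no answer for the false effect. If the five effects were scored separately, the always-alarming student would get 6.2 of 12 against 4.95 by guessing, a difference of 1.25/12 = 10 points.

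The cost is the loss of the present item 3, a possibly smaller reported gain, and IRB review. The budget in section 10 lists $312 per document of subject materials (2 × 312 = $624 if both forms count), or $448.50 if the change is treated as a protocol amendment without revised consent. The documents do not show whether the forms are already in use; if they are, only the separate reporting remains, with items 4 and 5 as they stand.

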## 1. INTRODUCTION

### 1.1. Background:

Adolescent use of vaporizers has increased rapidly in recent years in the United States. According to a survey taken by the National Public Radio (NPR) in November 2019, vaping amongst high school students has increased since 2016, in which approximately 12 percent of high school students reported using vaping products compared to 28 percent in 2019 (NPR, 2019). NPR stated that as of 2019, 5.3 million teenagers use e-cigarettes daily (NPR, 2019). According to American Lung Association, about 40 percent of kids have tried vaping. Further, it is likely their parents do not know as vaping is easy to hide compared to traditional cigarettes (American Lung Association, 2019).

Unfortunately, vaping does not stop after high school. Vape usage has increased on college campuses even with nationwide smoking bans on every campus. According to a survey done by Inside Higher Ed, it was found that the use of- e-cigarettes, vape marijuana, and vape nicotine has doubled among college students between the years of 2017 to 2018 (IHE, 2019). However, the use of vaporizers in the adult (25 to 44) age group is lower compared to the younger population due to the recent popularity of vaping products (Truth Initiative, 2019).

Vape products contain aerosol and approximately 7,000 chemicals; at least 70 of these chemicals are known to cause cancer (American Cancer Society, 2018). Due to nicotine being a highly addictive substance and prominent in many vaping products, individuals that smoke vape pens are four times more likely to

use tobacco products and smoke cigarettes (Truth Initiative, 2019). E-cigarettes or vaping products use- associated lung injury (EVALI) has been reported. Many individuals are being diagnosed with cancers of the lung, mouth, bronchi, and throat.

The Centers for Disease Control and state agencies have reported 2,506 lung injury cases that required hospitalization and 54 deaths linked to vaping as of December 2019 (CDC, 2019). According to John Hopkins, on January 7, 2020, there were 57 deaths that were linked to vaping. That number increased to 60 on January 21, 2020 (John Hopkins, 2020)

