**2. OBJECTIVES AND STUDY OUTCOME MEASURES**

**2.1.** Study Objectives

**2.1.1.** Primary Objective(s)

The primary objective for this program is to obtain an understanding and gather information on the percentage of vape users in teens and young adults. This study will include at least 100 individuals, as this will allow us to determine why vaping is so prominent, what causes individuals to be attracted towards this habit, and determine why there is an increasing rate of vaping.

**2.1.2.** Secondary Objective(s)

The secondary objective for this program is to prevent those who do not vape to not begin to partake in this habit and to reduce the percentage pf the target population who are currently vaping, by increasing their knowledge on the dangers of vaping by 10%.

**2.2.** Study Outcome Measures

**2.2.1.** Primary Outcome(s)

We will obtain the percentage of vape users and their reasons for vaping from information gathered from pre-test (Appendix C). Within 6 months, we hope to see a decline in the usage of vapes in the DFW area.

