## Appendix B: Data Collection Tool

## Excel Spreadsheet: Pre-Test

## Excel spreadsheet: Post-Test

## Appendix C

### Pre-Test

1. Do you or have you ever smoked tobacco cigarettes?
  - a. Yes, I currently smoke
  - b. Yes, I smoked in the past
  - c. No, I never smoked
2. Do you or have you ever used a vape pen, e-cigarette, or other vaping products?
  - a. Yes, I currently use these products
  - b. Yes, I have tried these products in the past
  - c. No, I never used these products
3. How often do you vape?
  - a. Everyday
  - b. 3 to 5 times a week
  - c. Once a week
  - d. Few times a month
  - e. Never
4. How long have you been vaping and/or using tobacco products?
  - a. Less than 3 months ago
  - b. 6 months ago
  - c. About 1-2 years ago
  - d. More than 2 years ago
  - e. I never have
5. Using vaping products will help you stop smoking cigarettes?
  - a. True
  - b. False
6. Using vaping products may cause harm to my health?
  - a. True
  - b. False
7. By using vaping products, I am more likely to smoke cigarettes in the future.
  - a. True
  - b. False
8. There are currently \_\_\_\_ million students that use vaping products
  - a. 1 million
  - b. 3.5 million
  - c. 8 million
  - d. 5.3 million
9. Students who vape are \_\_\_\_ more likely to begin smoking cigarettes
  - a. twice

b. four times  
c. five times  
d. ten times

10. There are at least \_\_\_\_ confirmed vape related deaths as of January 21st, 2020  
a. 15  
b. 35  
c. 60  
d. 2

11. People vape because \_\_\_\_  
a. It helps them to relax  
b. Their friends or family vape  
c. They like the taste of it  
d. They think it is safer than tobacco cigarettes  
e. All the above

12. I feel pressured to vape.  
a. Yes  
b. No  
c. Sometimes

13. Effects that vaping has on my body are \_\_\_\_  
a. Decreased brain development  
b. Problems with breathing  
c. Increase heart rate  
d. Higher chance of developing cancer  
e. All the above

14. How likely are you to use vaping products?  
a. Not at all  
b. Not sure  
c. Very likely  
d. I already vape

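### Post-test item 3 (pre-test item 7) asks for a fact in the first person, so a student who does not vape can truthfully answer False and lose a knowledge point

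*Combined protocol and SAP*

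**What the plan says.** Section 1.2, objective 3, makes the pre-test the baseline and the post-test the measure of effectiveness, and adds that "the goal is to have the students answer at least 8 out of the 10 questions correctly". Section 2.2.2 states that "Changes in the degree of understanding will be assessed from the results of the pre- and post-test (Appendix C"). Section 2.1.2 aims to act on vaping "by increasing their knowledge on the dangers of vaping by 10" percent.

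Post-test item 3, repeated as pre-test item 7, reads "By using vaping products, I am more likely to smoke cigarettes in the future" and offers True or False only. Post-test item 5 (pre-test item 9) asks for nearly the same fact about students who vape in general, with 'four times' among its options. Section 1.1 gives the four-times figure.

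Three other items carry personal wording:
- Post-test item 1 (pre-test 5): "Using vaping products will help you stop smoking cigarettes", True or False.
- Post-test item 2 (pre-test 6): "Using vaping products may cause harm to my health", True or False.
- Post-test item 9 (pre-test 13): "Effects that vaping has on my body are", followed by four harms and an option for all of them.

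No section gives an answer key, a list of scored items, or an instruction for students who neither vape nor smoke.

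**The concern.** A knowledge item should have one correct answer for every respondent. Item 3 does not, if it is read as a question about oneself. A student who does not vape and has no intention of smoking can mark False and be telling the truth. The same student can mark 'four times' on item 5 without contradiction. That pair of answers shows that the fact is known, yet it would cost a point on item 3.

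A personal reading is realistic on these forms. Pre-test items 1 to 4 ask about the student's own smoking and vaping and come shortly before item 7. Post-test item 8 (pre-test 12), on feeling pressured, is also in the first person and can only be personal.

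At stake is what the score means. The 8-of-10 goal would partly count how students read a pronoun. The pre/post change could mix learning with personal intention if the reading moved between the two tests.

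**Working it through.** **The plan's own figure.** The plan has no figure for item scoring. Its one calculation, in section 5.1, does not enter here. Its attrition step reproduces: 35 / 0.80 = 43.75, rounded up to 44.

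**Inputs.** Section 1.1 says that "approximately 12 percent of high school students reported using vaping products compared to 28 percent in 2019", so about 100 - 28 = 72% of high school students do not vape. It also says that about 40% of kids have tried vaping, so about 60% never have. Both are background figures, not measurements of this sample. No cigarette-smoking prevalence is given.

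**Item by item, for a student who neither vapes nor smokes and answers personally**

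| Post-test item | Personal answer | Implied key | Result |
|---|---|---|---|
| 1 | False | probably False | credit possible without knowledge |
| 2 | True is easy to give, because the stem says 'may' | True | little harm |
| 3 | False | True (section 1.1) | point lost without lack of knowledge |
| 9 | no option fits | all of the above | blank or hypothetical answer |

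Only item 3 turns a true personal answer into a wrong one.

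**The 8-of-10 goal.** Assume that items are independent and each is known with probability p. Items 8 and 10 ask about pressure and intention and have no correct answer, so there are two cases.

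- *Items 8 and 10 earn no credit.* All eight other items are needed: P = p^8 = 0.168, 0.430 and 0.663 at p = 0.80, 0.90 and 0.95. A False on item 3 leaves at most 7, so P = 0.
- *Items 8 and 10 are always credited.* Six of eight are needed: P = p^8 + 8p^7(1-p) + 28p^6(1-p)^2 = 0.797, 0.962 and 0.994. With item 3 lost, six of seven are needed: P = p^7 + 7p^6(1-p) = 0.577, 0.850 and 0.956.

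For the whole group, let s be the share of non-vapers who answer item 3 personally, so the affected share of students is f = 0.72s. At p = 0.90, with s assumed:

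| s | f | No credit: 0.430(1-f) | Credited: 0.962 - f(0.962-0.850) |
|---|---|---|---|
| 0% | 0 | 0.430 | 0.962 |
| 10% | 0.072 | 0.399 | 0.954 |
| 25% | 0.18 | 0.353 | 0.942 |
| 50% | 0.36 | 0.275 | 0.922 |

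**The paired change.** A student who reads item 3 personally on both forms marks False twice and contributes zero change. That adds no downward shift, although the item cannot then register learning in that student. Only a net move to a personal False between the tests lowers the mean change. On an assumed eight-item score, one item is 100/8 = 12.5 points. If a share q of non-vapers makes that move:

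loss in mean change = 0.72 x q x 12.5

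- q = 5%: 0.45 points
- q = 10%: 0.90 points
- q = 20%: 1.80 points

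With 60% in place of 72%, the ends of the range are 0.60 x 0.05 x 12.5 = 0.375 and 0.60 x 0.20 x 12.5 = 1.5. On a ten-item score with 72%, they are 0.72 x 0.05 x 10 = 0.36 and 0.72 x 0.20 x 10 = 1.44.

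**The case against.** The strongest reply is that item 3 is conditional. It opens with the act of using vaping products, so a non-vaper can take it as 'if I used them' and answer True. That stands as a possible reading. It means that the share answering personally is unknown and may be small; it does not make the wording safe.

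A second reply is that both forms use identical wording, so a stable reading cancels in the paired analysis of section 5.2. This also stands, but it gives no protection to the 8-of-10 goal, which uses the post-test only.

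A third is that item 5 already measures the fact neutrally. True, but item 3 would still cost a point in the same score.

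A reader might infer that items 1, 3 and 9 all mark most students wrong. The documents do not support this. On item 1 a non-smoker's personal False probably matches the key, so the error runs towards unearned credit. Item 1 says 'you', which can be read generally, and its affected group depends on a smoking prevalence that is not given. Item 9 has no personal answer that could be marked wrong. Nor does a non-vaping majority mean that a majority is affected: not vaping is not the same as answering personally.

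A reader might also infer that the talk pushes item 3 towards False because it strengthens resolve. The stated behavioural aims (sections 1.2, 1.4.1 and 2.1.2, and Appendix D) concern vaping, while item 3 asks about future cigarette smoking. Such a shift is conceivable, but no section documents it.

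**Conclusion.** The point holds for item 3. It is a first-person True/False statement used as a knowledge question, and a non-vaper can answer it truthfully against the implied key. Items 1, 2 and 9 have related but lesser wording faults.

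The effect falls mainly on the 8-of-10 goal. For a student who knows each item with probability 0.90, a personal False on item 3 lowers the chance of reaching the goal from 0.962 to 0.850 if items 8 and 10 are credited, and from 0.430 to 0 if they are not. The group effect depends on an unknown share of personal readers. For the paired change the loss is about 0.45 to 1.8 percentage points, and only if 5% to 20% of non-vapers shift to a personal False between the tests.

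These figures rest on assumptions: the shares themselves, independence of items, the 28% high school figure applied to a sample that also includes middle school and college students, and an eight-item score that no section defines. That False on item 3 would be scored wrong is inferred from section 1.1, because no key is written down. The 10% in section 2.1.2 may be relative or in points, so the loss should not be read as a fixed fraction of that target. The primary outcome in section 2.2.1 and objective 4 in section 1.2 are not affected.

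**What to change.** Before the forms are used, reword item 3 in the third person, identically on both tests, for example: 'Using vaping products makes a person more likely to start smoking cigarettes.' For consistency, do the same for items 1, 2 and 9: ask item 1 about people in general, replace 'my health' in item 2 with a person's health, and replace 'my body' in item 9 with 'the body'.

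If any session has already used the present forms, leave item 3 out of the knowledge score for all sessions, so that every student is scored on the same number of items, and report item 3 separately.

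The cost is a few words on each paper form and IRB review of the revision, which section 6.2 requires. No items, session time or participants are added. The downside is that, if the old forms were used, item 3 is lost from the score and the 8-of-10 goal has to be restated for the items that remain.

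### Three knowledge items on the test forms can be misclassified: an 'at least' stem, a figure that does not match its source, and two post-test options lettered d

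*Combined protocol and SAP*

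**What the plan says.** Objective 3 in Section 1.2 sets the target for the post-test: "the goal is to have the students answer at least 8 out of the 10 questions correctly". Section 2.2.2 makes the score a secondary outcome: "Changes in the degree of understanding will be assessed from the results of the pre- and post-test". The text provided contains no answer key, and Appendix B shows only the headings of its two spreadsheets. Under Section 7.4, answers are given on paper and transferred to Excel.

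The three items in Appendix C are:

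- **Deaths** (post-test item 6, pre-test item 10). The stem asks for at least how many "confirmed vape related deaths as of January 21st, 2020", with options 15, 35, 60 and 2. Section 1.1 supplies the figure: "That number increased to 60 on January 21, 2020".
- **Number of users** (post-test item 4, pre-test item 8). The stem asks for the number of "million students that use vaping products", with options 1, 3.5, 8 and 5.3 million. Section 1.1 states that "5.3 million teenagers use e-cigarettes daily".
- **Reasons for vaping** (post-test item 7, pre-test item 11). On the post-test, "They think it is safer than tobacco cigarettes" is option d, and the next line reads "d. All the above". On the pre-test the last option is lettered e.

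**The concern.** A knowledge score is useful only if each item separates students who know the fact from those who do not. Here the three items can fail in different ways. The first has a stem that several options satisfy. The second asks about a quantity that the protocol's source figure does not measure. The third has an answer code that stands for two options on one of the two forms. A student's answer could then be scored in a way that does not reflect what the student knows. At stake are the share of students who reach 8 of 10 and the paired pre/post comparison. The primary outcome in Section 2.2.1 (percentage of vape users and their reasons, from the pre-test) does not use these scores.

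**Working it through.** **Sample size (background).** Section 5.1 gives 35, then 44. With dz = 0.5, two-sided alpha 0.05 and a Wilcoxon efficiency of 3/pi, n = 35 gives power 0.801, and 35 / 0.80 = 43.75, rounded up to 44. Both figures reproduce. Nothing below depends on them.

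**Deaths item.** Take 60 deaths as given. 'At least X' is true whenever X is 60 or less. The options 2, 15, 35 and 60 all qualify, so 4 of 4 are literally true.

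**Users item.** Stem and source compare as follows.

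| | Population | Definition of use | Figure |
|---|---|---|---|
| Section 1.1 | teenagers | daily | 5.3 million |
| Item stem | students | use, frequency not stated | to be chosen |

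Daily users are a subset of all users. If Section 1.1 is right as written, 5.3 million is a floor for any use among teenagers, and the documents cannot exclude the 8 million option. If 'daily' is itself a slip, the stem may be right and Section 1.1 wrong. The documents do not settle which. The Appendix D outline contains no 5.3 million figure.

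**Reasons item.** Let p be the share of post-test answers recorded only as d, and s the share of those that meant the all-inclusive option (assumed to be the key).

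- If d is scored wrong, the post-test proportion correct is too low by p × s.
- If d is scored right, it is too high by p × (1 − s).

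The pre-test lettering is clean, so either error passes straight into the change for this item. The documents give neither p nor s. If students circle an option and its text is entered, p = 0 and there is no error.

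**Where each fault acts.** The first two items are worded identically on both forms, so their ambiguity is present at both times and mainly adds misclassification. Only the lettering fault differs between the forms.

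**Share of the score.** Post-test items 8 (feeling pressured) and 10 (likelihood of use) are self-report and have no factual answer.

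- All 10 items counted: 3/10 = 30%.
- Items 8 and 10 not scored: 3/8 = 37.5%.

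If a fraction f of students is mis-marked on an item, the mean score falls by f items. For example, f = 10% gives 0.1 item per affected question. This is an identity, not an estimate of f.

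**Effect on the 8-of-10 goal.** Take a student who knows everything. Let q be the assumed chance that each of the three items is marked as keyed, independently. If items 8 and 10 earn no credit, the goal needs all eight remaining items, so P(reach goal) = q³. If both are credited to everyone, the student falls short only by losing all three, so P = 1 − (1 − q)³.

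| q (assumed) | Items 8, 10 uncredited: q³ | Items 8, 10 credited: 1 − (1 − q)³ |
|---|---|---|
| 0.90 | 0.729 | 0.999 |
| 0.75 | 0.422 | 0.984 |
| 0.50 | 0.125 | 0.875 |

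The scoring convention matters at least as much as q.

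**The case against.** The strongest reply is that these are proofreading faults with little practical effect. 'At least 60' is ordinary phrasing for a count that may rise. Section 1.1 gives 60 for the very date in the stem, and a student who knows the figure will choose 60. Choosing 2, 15 or 35 does not demonstrate knowledge. For the users item, 5.3 million is the only option that matches a figure in the protocol. For the reasons item, the two options differ in text and position, so a circled answer is clear. The duplicate letter could also come from how the PDF was read. That item may not be meant as a scored one at all, since Section 2.2.2 lists reasons for vaping as a descriptive question.

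Most of this stands, and it limits the size of the point. It does not remove the faults: no key is shown that would settle an odd answer, and the documents do not say whether answers are recorded by letter or by text.

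A reader might also infer that all three items lack a unique correct answer. The documents do not support that. The users item offers four distinct totals, of which at most one can be right; its fault is a mismatch with the source. In the reasons item the fault lies in the lettering, not in the content.

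**Conclusion.** The point holds as a minor one. Three post-test items, two of them worded identically on the pre-test, can be misclassified, and they feed a stated goal and a secondary outcome. The affected share is 30% of the items, or 37.5% if items 8 and 10 are not scored.

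A reader might go further and conclude that one mis-marked answer puts the goal out of reach, or that the lettering does bias the paired change. Neither follows. The first assumes that items 8 and 10 earn no credit, whereas Section 1.2 speaks of 10 questions and gives no scoring rule. The second requires answers to be recorded by letter alone, and its direction depends on how d is then scored.

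The conclusion rests on these assumptions: 60, 5.3 million and the all-inclusive option are the intended keys; item 7 is scored; and the lettering in the text provided matches the printed form. The values of q are illustrative, because the documents give no error rate.

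**What to change.** - Remove 'at least' from the deaths item on both forms.
- Check the 5.3 million figure against its source. Then use the same population and the same definition of use in Section 1.1 and in the item on both forms.
- Check the lettering of post-test item 7 on the original form. If the duplicate is real, letter the last option e, as on the pre-test.

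It would also help to record, before scoring, the answer key and which of the 10 items count.

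Cost: a few wording edits if made before the forms are approved and printed. If they are already approved, Section 6.2 requires IRB review of any amendment before the change is made. Section 10 lists $345 per site for an amendment without a revised consent ($448.50 with the 30% indirect cost), and $240 per document for review of subject materials ($312). The documents do not say which of these fees would apply.
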